### **11.2.6 Population PK Analysis**

The PK endpoint is individual model parameter estimates of rucaparib and covariates identification.

A specific population PK data analysis plan will be developed that will outline the detailed approach to data handling, model development and diagnostics, individual model parameter estimation, exploration of covariate effects, and final model evaluation techniques.

### **11.2.7 Exploratory Analyses**

The endpoints for the exploratory analyses are:

- Change from baseline in CA-125 measurements by the central laboratory
- PFS2 (PFS on the subsequent line of treatment) defined as the time from randomization to the second event of disease progression or death, as assessed by the investigator
- ORR per RECIST v1.1, as assessed by both the investigator and IRR, in patients with measureable disease at study entry
- DOR per RECIST v1.1, as assessed by both the investigator and IRR
- PRO as measured by the EQ-5D total score
- Rucaparib PK, invPFS, irrPFS, CA-125, AEs, clinical laboratory abnormalities, and dose modifications

### **11.2.7.1 Change from Baseline in CA-125**

Analyses of changes and/or percent changes from baseline will be analyzed for each scheduled post-baseline visit and for the final visit for the CA-125 measurements from the central laboratory. Patients that do not have both a baseline measurement and at least one post-baseline measurement will not be included.

At a given visit, the change and/or percent change from baseline will be compared between the randomized treatment groups using an ANCOVA using the treatment as a categorical factor and baseline measurement for the parameter as a continuous covariate.

The association between the change from baseline in CA-125 measurements and invPFS will be evaluated using a Cox proportional hazards model. A measure of CA-125 kinetics such as the rate of change from baseline in CA-125 may also be associated with invPFS using a Cox model.

### **11.2.7.2 Progression Free Survival 2 (PFS2)**

The second event of PFS, PFS2, is defined as the time from randomization to the second event of disease progression as assessed by the investigator, or death due to any cause. The first event of disease progression will be captured as the primary endpoint in this study and thus the second event will be the next event of disease progression as assessed by the investigator. This second event of PFS may be a documented event per RECIST guidelines or may be an event of symptomatic progression.

### **11.2.7.3 Overall Response Rate**

ORR is defined as a best response of CR or PR using the RECIST v1.1 criteria ([Appendix B](#)), as assessed by both investigator and IRR, in patients with measurable disease at study entry. ORR will be summarized with frequencies and percentages in the safety population.

### **11.2.7.4 Duration of Response**

The DOR is measured from the time measurement criteria are met for CR/PR per RECIST v1.1 criteria ([Appendix B](#)), as assessed by both the investigator and IRR, until the first date that recurrent or progressive disease (PD) is objectively documented. The DOR will be summarized with descriptive statistics. Only patients with a response will be included in the summary.

### **11.2.7.5 Patient Reported Outcome EQ-5D**

Analyses of changes and/or percent changes from baseline will be analyzed for each scheduled post-baseline visit and for the final visit for the EQ-5D instrument. Patients that do not have both a baseline measurement and at least one post-baseline measurement will not be included.

At a given visit, the change and/or percent change from baseline will be compared between the randomized treatment groups using an ANCOVA using the treatment as a categorical factor and baseline measurement for the parameter as a continuous covariate.

### **11.2.7.6 Relationship between Rucaparib Exposure and Efficacy and Safety**

The primary endpoint of invPFS will be presented for subgroups of patients defined by levels of rucaparib exposure. These analyses are exploratory in nature so the definition of relevant subgroups may be data-driven.

## **11.3 Interim Analysis**

No formal interim efficacy analyses will be performed.

All endpoints were summarized at the time the primary endpoint (invPFS) was unblinded in April 2017; however, the following efficacy endpoints are still being collected and will be summarized at the time of the study closing:

- Secondary Endpoint of Final OS
- Post-progression exploratory endpoints (PFS2, time to first subsequent anticancer treatment, time to second subsequent anticancer treatment, and chemotherapy-free interval)

The OS data were heavily censored at the time of the primary endpoint analysis. In order to adjust for multiple analyses of OS at a later stage, a stopping rule will be applied. The Haybittle-Peto stopping rule will be applied, where an OS result with a p-value < 0.001 can be used to claim superiority of rucaparib compared to placebo. This means that a p-value < 0.05 can be utilized at the final analysis, which is projected to occur once 70% of the death events have been collected.

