### 11.2 Statistical Methods

#### 11.2.1 General Considerations

Variables registered on a continuous scale will be presented using the following descriptive statistics: N, mean, standard deviation, median, minimum and maximum. Continuous variables may also be presented using frequencies and percentages among appropriate categorizations. Categorical variables will be presented using frequencies and percentages. The Kaplan-Meier methodology will be used to summarize time-to-event variables. The number of patients with events and the number of censored patients will also be presented. The stratified logrank test will be used to compare the time-to-event distributions between the randomized treatment groups. In addition, the Cox proportional hazards model will be used to estimate the HR between the randomized treatment groups.

The primary and key secondary endpoints will be tested among the tBRCA and all HRD subgroups, and all randomized patients, using an ordered step-down multiple comparisons procedure. Investigator determined PFS (invPFS) in the tBRCA subgroup will be tested first at a one-sided 0.025 significance level. If invPFS in the tBRCA subgroup is statistically significant, then invPFS will be tested in the all HRD subgroup followed by invPFS in all randomized patients. Continuing in an ordered step-down manner, the PRO of disease symptoms utilizing the FOSI-18 DRS-P subscale will be tested at the one-sided 0.025 significance level in the tBRCA, all HRD, and all randomized patients subgroups and then for the remaining key secondary endpoints of PRO utilizing the FOSI-18 total score and OS. Once statistical significance is not achieved for one test the statistical significance will not be declared for all subsequent analyses in the ordered step-down procedure.

PFS by IRR will be evaluated as a stand-alone secondary endpoint.

All data will be used to their maximum possible extent but without any imputations for missing data.

All statistical analyses will be conducted with the SAS® System, v9.1 or higher.

Unless otherwise specified, baseline is defined as the last measurement on or prior to the first day of study drug administration.

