##### ***Overall survival***

Overall survival (OS) is defined as the number of days from the date of randomization to the date of death (due to any cause). Patients without a known date of death will be censored on the date the patient was last known to be alive.

An interim OS was determined at the time of the primary endpoint unblinding ([Section 11.3](#)). The final OS analysis will be performed at the time of the study close. See [Section 11.3](#) for further details.

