9.3 Secondary Efficacy Variables Not Included in the Step Down Analysis

- Interim OS
- Independent Radiology Review Determination of PFS

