10.3 Secondary Efficacy Analyses Not Included in the Step Down Procedure

10.3.1 Overall Survival

The time to overall survival will be calculated in months as the time from randomization to date of death due to any cause. Patients who are still alive will be censored on the date of their last available visit or last date known to be alive.

It is anticipated that the data for overall survival will be heavily censored at the time of the primary endpoint analysis. In order to adjust for multiple analyses of overall survival at a later stage, a stopping rule will be applied. The Haybittle-Peto^{3, 4} stopping rule will be applied where an overall survival result with a p-value <0.001 can be used to claim superiority of rucaparib compared to placebo. This means that a p-value <0.05 can be utilized at the final analysis which is projected to be once 70% of the death events has been collected.

The same statistical test used for the primary endpoint (i.e., stratified log rank test and a stratified Cox proportional model) will be used to compare rucaparib to placebo for this endpoint.

10.3.2 Population PK: Individual Model Parameter Estimates of Rucaparib and Covariates Identification.

A population PK analysis will be performed and documented in a separate report.

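### The SAP puts interim OS outside the step-down yet allows a superiority claim from it at p<0.001, in conflict with Protocol 11.2.1, which places OS last in the step-down

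*Protocol*

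**What the plan says.** - **Protocol 11.2.1** sets an ordered step-down at one-sided 0.025: invPFS, then the DRS-P subscale, then the FOSI-18 total score and OS, tested among tBRCA, all HRD and all randomized patients. Interim and final OS are not distinguished. The gate reads: "Once statistical significance is not achieved for one test the statistical significance will not be declared for all subsequent analyses".
- **Protocol 11.3** opens with "No formal interim efficacy analyses will be performed". It then applies Haybittle-Peto to OS, "where an OS result with a p-value < 0.001 can be used to claim superiority of rucaparib compared to placebo". For the later look it adds: "This means that a p-value < 0.05 can be utilized at the final analysis". The timing of that look is tied to 70% of deaths.
- **Protocol 11.2.4.2** (Overall survival) records that the first look has been taken: "An interim OS was determined at the time of the primary endpoint unblinding".
- **SAP 9.2** lists final OS among the step-down variables. **SAP 9.3**, headed "Secondary Efficacy Variables Not Included in the Step Down Analysis", lists interim OS together with PFS by independent radiology review.
- **SAP 10.3.1** repeats that "an overall survival result with a p-value <0.001 can be used to claim superiority of rucaparib compared to placebo". It describes both OS looks, including the final threshold, and sits under the 10.3 heading for analyses outside the step-down.

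Neither statement of the 0.001 rule makes it conditional on an earlier test, names a population or gives a sidedness.

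**The concern.** Nine tests stand ahead of OS: invPFS, DRS-P and FOSI-18 total, each in three nested populations. If one fails, SAP 9.2 and Protocol 11.2.1 bar a final OS claim. Because SAP 9.3 takes interim OS out of the procedure to which the gate applies, SAP 10.3.1 can be read as still allowing an interim claim. Suppose DRS-P fails in tBRCA. An interim OS p of 0.0009 could then be claimed as superiority, while the same p at the final analysis, on more deaths, could not. The less mature look would have the easier route to a survival claim.

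Haybittle-Peto does not settle this. It handles repeated looks at OS, not the place of OS behind other endpoints. The step-down already uses the whole one-sided 0.025, so an extra ungated route to a confirmatory claim must add to it.

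**Working it through.** **1. Inputs**

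| Input | Value | Source |
|---|---|---|
| Step-down level | one-sided 0.025 | Protocol 11.2.1, SAP 3.3 |
| Interim OS threshold | 0.001, sidedness not stated | Protocol 11.3, SAP 10.3.1 |
| Final OS threshold | 0.05, sidedness not stated | same |
| Planned N: tBRCA / HRD / ITT | 180 / 300 / 540 | Protocol 11.4, SAP 2.3 |
| OS deaths, interim information fraction | not given | assumed below |

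The final 0.05 matches the step-down only if it is two-sided, which suggests that 0.001 is two-sided too (one-sided 0.0005). Both readings are shown.

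**2. The plan's own figure.** In a fixed sequence with every claim gated, the family-wise error is the level at which the first true null is tested. That is 0.025, as stated.

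**3. Is interim OS gated?**

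| Text | Interim OS | Final OS |
|---|---|---|
| Protocol 11.2.1 | in step-down (looks not separated) | in step-down |
| SAP 9.2 / 9.3 | outside | inside |
| SAP 10.3 heading over 10.3.1 | outside | outside |
| Protocol 11.3 / SAP 10.3.1 rule | may support a claim | may support a claim |

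The documents give no single answer.

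**4. Error if interim OS is ungated.** Take the case where PFS works, but DRS-P in tBRCA (the first true null) and OS are null, with OS independent of DRS-P. Then

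FWER = 1 − (1 − 0.025)(1 − p), where p is the chance that interim OS crosses.

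*One population:*
- two-sided 0.001: 1 − 0.975 × 0.9995 = 0.0255
- one-sided 0.001: 1 − 0.975 × 0.999 = 0.0260

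*Any of three nested populations.* Assume deaths proportional to planned N. The correlations are √(180/300) = 0.77, √(300/540) = 0.75 and √(180/540) = 0.58. The trivariate normal gives:
- P(any Z > 3.29) = 0.00130, so FWER = 1 − 0.975 × 0.99870 = 0.0263
- P(any Z > 3.09) = 0.00254, so FWER = 1 − 0.975 × 0.99746 = 0.0275

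Simple addition, which needs no assumption about dependence, bounds the three-population cases at 0.025 + 3 × 0.0005 = 0.0265 and 0.025 + 3 × 0.001 = 0.0280.

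**5. Error once interim OS is gated.** The bypass term disappears. For OS itself, looks at one-sided 0.0005 and 0.025 (bivariate normal, correlation equal to the square root of the information fraction) total 0.0254 at fraction 0.1, 0.0251 at 0.5 and 0.0250 at 0.9. Holding the total at exactly 0.025 would need a final level of about 0.0247 to 0.0250 for fractions 0.2 to 0.7.

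**The case against.** The protocol taken alone gates OS. Section 11.2.1 puts OS in the step-down without distinguishing looks, and 11.3 brings in Haybittle-Peto to adjust for repeated OS analyses; it nowhere waives the gate. A reader might infer that Protocol 11.3 by itself lets OS bypass a failed test. The text does not support that: the bypass appears only when the rule is combined with SAP 9.3. This part of the objection stands.

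SAP 9.3 can also be read as making interim OS merely supportive. That is plausible, but SAP 10.3.1 then attaches a superiority claim to it. The SAP's headings do not decide the matter either: 10.2.3 describes PFS by independent review as inside the step-down, while 9.3 lists it as outside.

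A reader might further infer that significance in any one population would suffice. No rule says so. The general defaults differ (ITT in Protocol 11.2.4; the three nested groups in SAP 3.3), so the three-population figures describe a worst case. SAP Figure 1, which illustrates the step-down, is not shown in the text reviewed and might settle the order. If it gated interim OS, it would still conflict with 9.3.

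The opening sentence of Protocol 11.3 is a weaker point. The protocol synopsis limits the same statement to early stopping, so the contradiction is largely one of wording.

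Finally, the look is past, so a rule written now is retrospective. That is right, and it limits what the edit may do.

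**Conclusion.** The conflict is real, and worth correcting because it concerns a survival claim. Under the SAP as written, an interim OS claim is not tied to the earlier tests and has no population order; under Protocol 11.2.1 it is tied to them. Two careful readers could reach opposite conclusions from the same interim p-value.

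The cost in error is small: 2.55% to 2.63% against 2.5% on the more likely two-sided reading of 0.001, and 2.60% to about 2.75% on the one-sided reading. These figures rest on independence between OS and the failed test and, for three populations, on deaths proportional to planned N. Positive dependence would lower them. A reader might infer a serious loss of type I error control, or that an ungated OS claim was in fact made. The figures do not show the first, and the documents do not report the second.

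**What to change.** Amend Protocol 11.3 and SAP 9.2, 9.3 and 10.3.1 together:

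1. Put both OS looks in the step-down. Remove interim OS from SAP 9.3, and move 10.3.1 out from under the heading for analyses outside the step-down.
2. State that interim OS supports a claim only if every earlier test was significant. It is then tested in the order tBRCA, HRD, ITT at two-sided 0.001 (one-sided 0.0005). Otherwise it is descriptive.
3. State that a non-significant interim OS does not block final OS, as the Haybittle-Peto rule already implies. Final OS is tested in the same order at two-sided 0.05 (one-sided 0.025), with the small two-look excess shown above acknowledged.
4. Reword the opening sentence of Protocol 11.3 so that it excludes the OS look.
5. Check SAP Figure 1 against the revised text.

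Because the interim look followed unblinding and has already taken place, record the amendment as post-unblinding and as one that only restricts what may be claimed. The cost is wording in two documents. The downside is that the sponsor gives up an ungated interim OS claim, which its own step-down would refuse at the final analysis.

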## **11.4 Sample Size Considerations**

The total enrollment planned is 540 patients. A minimum of 180 and a maximum of 200 patients with a deleterious tBRCA mutation will be enrolled. Enrollment of patients with a known deleterious gBRCA mutation documented in their medical record will not exceed 150. There is no minimum number of patients required for each of the nbHRD and biomarker negative subgroups; however, no more than 360 total patients will be randomized for stratification into these subgroups combined. Prior to final efficacy analysis, HRD classification will be determined by the FCTA, which will evaluate homologous recombination gene mutations and/or extent of genomic scarring in tumor tissue.

[Table 4](#) below provides estimated sample sizes and power calculations.

**Table 4. Estimated Sample Sizes and Power Calculations**

Group	Hazard Ratio	Cumulative N	Minimum Number of Events (70%)	Median PFS Placebo vs Rucaparib (months)	Power	One-sided Alpha
BRCA HRD	0.50	180	126	6 vs 12	90%	0.025
All HRD (BRCA + nbHRD)	0.60	300	210	6 vs 10	90%	0.025
ITT Population (BRCA + nbHRD + Biomarker Negative)	0.70	540	378	6 vs 8.5	90%	0.025

The study will end after 70% of the patients in the tBRCA subgroup have an observed event of investigator-determined disease progression or death. If the minimum number of tBRCA patients are enrolled, then the study will end following the 126th event of investigator-determined disease progression or death. Similarly, if the maximum number of tBRCA patients are enrolled, then the study will end following the 140th event of investigator-determined disease progression or death. The IDMC will inform the sponsor when the required number of PFS events have been observed in order to ensure the sponsor remains blinded to which patients are in the tBRCA subgroup. If the nbHRD and/or biomarker negative subgroups have observed events of invPFS in fewer than 60% of the patients, the IDMC may recommend that the study continue for up to 6 more months if it is likely that the nbHRD and biomarker negative subgroups will observe enough additional events of PFS to reach 60%.

Following the collection of the required number of PFS events, the outstanding queries for all visits and events prior to the data cutoff date will be resolved and the database will be locked before the blind break and subsequent primary analysis.

## **12 PATIENT DISPOSITION**

### **12.1 Removal of patients from therapy or assessment**

A patient must be discontinued from treatment with study drug if any of the following apply:

- Consent withdrawal at the patient's own request or at the request of their legally authorized representative
- Progression of patient's underlying disease by RECIST v1.1 as assessed by the investigator
- Any event, adverse or otherwise, that, in the opinion of the investigator, would pose an unacceptable safety risk to the patient
- An intercurrent illness that, in the opinion of the investigator, would affect assessments of the clinical status to a significant degree and requires discontinuation of therapy
- A positive pregnancy test at any time during the study.

The sponsor may discontinue the trial early for any of the reasons noted in [Section 13.7](#).

### **12.2 Procedures for discontinuation**

The sponsor (or designee) should be notified of all study terminations as soon as possible. The date and reason for cessation of study drug must be documented in the eCRF and source documents. To the extent possible, end-of-study procedures should be performed on all patients who receive study drug. The Treatment Discontinuation visit should occur 28 ( $\pm 3$ ) days following the last dose of study drug. Patients will be followed for 28 days after the last dose of study drug for safety; those with ongoing SAEs/AESIs will be followed until either resolution or stabilization has been determined.

## **13 STUDY ADMINISTRATION**

### **13.1 Regulatory and Ethical Considerations**

The study will be conducted in accordance with the protocol and applicable standard operating procedures (SOPs); and in compliance with applicable guidelines and regulations.

The investigator will assure that no amendments to the protocol will take place without prior agreement from the sponsor and documented approval from the IRB/IEC, and local health authority (where applicable), except where necessary to eliminate an immediate hazard(s) to the study participants.

Significant noncompliance with the protocol, SOPs, Good Clinical Practice (GCP), and/or applicable regulatory requirement(s) by an investigator/institution, or by member(s) of the sponsor staff or its representatives will lead to prompt action by the sponsor to secure compliance. If monitoring and/or auditing identifies serious noncompliance on the part of an investigator/institution, the sponsor will take steps to secure compliance or terminate the investigator's/institution's participation in the study. When an investigator's/institution's participation is terminated because of significant noncompliance, the sponsor will promptly notify the regulatory authority(ies) and other appropriate parties (eg, IRB/IEC).

All potential serious breaches of GCP must be reported to the sponsor or designee within 24 hours. A serious breach is a breach of the conditions and principles of GCP in connection with the study or the protocol, which is likely to affect, to a significant degree, the safety or physical or mental integrity of the participants of the study or the scientific value of the study.

Personnel involved in conducting this study will be qualified by education, training, and experience to perform their respective tasks.

This study will not use the services of study site personnel where sanctions have been invoked or where there has been scientific misconduct (eg, debarment).

### **13.2 Regulatory Authority Approvals**

The sponsor or designee will submit the study protocol plus all relevant study documents to concerned regulatory agencies for approval prior to the study start. No patient will begin study-specific screening until appropriate regulatory approval of the study protocol has been received.

Each investigator must complete a Form FDA 1572 (or equivalent, when participating in a US Investigational New Drug Application [IND] study). In addition, local statement of investigator documents must be provided where required. Each investigator must submit to the sponsor (or designee) financial disclosure information for studies under a US IND or if required by national law and/or local regulations.

The study will be registered on regionally-relevant registries, including [www.clinicaltrials.gov](http://www.clinicaltrials.gov), EU Clinical Trials Register, and other applicable trial registry systems as appropriate. Data generated from this study must be handled in accordance with any laws, rules, and regulations

related to the privacy of personal data or medical information applicable in the jurisdiction where the data is processed, including without limitation, the US Health Information Portability and Accountability Act of 1996 (HIPAA), and its implementing regulations, and the European Union General Data Protection Regulation 2016/679 (GDPR).

